10.3. Demographics, Disposition, and Baseline Characteristics

Subject enrollment and disposition, including reasons for early discontinuation from treatment and the study, will be summarized.

Baseline demographic (including sex, age, race, ethnicity, weight, height, body mass index) and disease characteristics will be summarized.

10.4. Methods of Analysis

In general, descriptive statistics, including numbers and percentages for categorical variables and numbers, means, standard deviations, medians, minimums, and maximums for continuous variables will be provided.

10.5. Statistical Analyses

10.5.1. Dose Escalation Algorithm

In Part 1, the dose escalation algorithm for the i3+3 design is rule-based and implemented by escalate (E), stay at the current dose (S) and de-escalate (D or DU), according to observed toxicities (Liu et al., 2020). Suppose dose d is the dose currently used to treat subjects, n_d is the number of subjects who have been treated at dose d , and x_d is the number of subjects who have experienced DLTs at dose d . The i3+3 design can be summarized as follows: at the current dose d , calculate two quantities x_d / n_d and $(x_d - 1) / n_d$. The decision rules compare these two quantities to the equivalence interval (EI), and depending on the comparison outcome, decide the next dose level for enrolling subjects.

- If x_d / n_d is below the EI, escalate (E) and enroll subjects at the next higher dose ($d + 1$);
 - else, if x_d / n_d is inside the EI, stay (S) and continue to enroll subjects at the current dose d ;
 - else, if x_d / n_d is above the EI, there are two scenarios:
 1. if $(x_d - 1) / n_d$ is below the EI, stay (S) and continue to enroll subjects at the current dose d ,
 2. else, de-escalate (D or DU) and enroll subjects at a lower dose ($d - 1$).

When d is the highest dose or the lowest dose, the above rules need to be modified as special cases.

- If the current dose is the highest dose, and x_d / n_d is below the EI, stay (S) instead of escalate (E) and continue to enroll subjects at the current dose. This is because there is no dose to escalate to.
- If the current dose is the lowest dose, and x_d / n_d is above the EI, stay (S) instead of potentially de-escalating (D or DU) and continue to enroll subjects at the current dose. This is because there is no dose to de-escalate to.

Following the mTPI and mTPI-2 designs, two safety rules are added as ethical constraints to avoid excessive toxicity:

- Safety rule 1 (early termination due to excessive toxicity at the lowest dose). In the special case of cohorts of size 1, this early stopping rule should not be applied until three or more patients have been evaluated at a dose.
 - The term, excessive toxicity at the lowest dose (dose 1) can be expressed mathematically as follows: assume $n_1 > 0$, if $Pr(p_1 > p_T | x_1, n_1) > \xi$, for a large probability ξ , say 0.95 has occurred. Where Pr is probability and p_1 , p_T , x_1 , and n_1 represent “DLT rate at dose 1”, “target DLT rate”, “# of DLT at dose 1” and “cohort size at dose 1” respectively.
- Safety rule 2 (dose exclusion): Suppose that the decision is to escalate from dose d to dose $(d + 1)$. If there is a high probability that there is an excessive toxicity at dose $(d + 1)$, ie, $Pr(p_{d+1} > p_T | x_{d+1}, n_{d+1}) > \xi$ for $\xi = 0.95$, then treat the next cohort of patients at dose d instead of $(d + 1)$, and dose $(d + 1)$ and higher doses will be removed from the trial. These doses will be marked as “DU” to indicate that they are Unacceptable to use in the trial anymore.

Under the i3+3 design, a trial is terminated either when a prespecified sample size is reached or according to Safety rule 1. [Table 1](#) provides a decision table in i3+3 design for up to 12 patients treated at a given dose with the targeted DLT rate $p_T=0.3$ and the equivalence interval (EI) = [0.25, 0.35].

10.5.2. Estimation of MTD

At the end of Part 1, the MTD selection under the i3+3 design follows the same procedure as in the mTPI and mTPI-2 designs ([Liu et al., 2020](#)). The MTD should be the dose that KZR-261's

DLT rate is closest to the prespecified target DLT rate and within the equivalence interval (EI); to select the dose as the estimated MTD with the smallest difference: $|\hat{p}_d^* - p_T|$ among all the doses d for which $n_d > 0$ and $Pr(p_d > p_T | x_d, n_d) < \xi$. Here \hat{p}_d^* is the isotonically transformed posterior mean of p_d , the same as that in the mTPI design (Zhou and Ji, 2020). If two or more doses tie for the smallest difference, perform the following rule. Let p^* denote the transformed posterior mean \hat{p}_d^* of the tied doses.

- If $p^* < p_T$, choose the highest dose among the tied doses.
- If $p^* > p_T$, choose the lowest dose among the tied doses.

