2.2. Study Endpoints

2.2.1. Primary Endpoints

2.2.1.1. Safety – Part 1

Safety endpoints include the following:

- Incidence of dose-limiting toxicities (DLTs) during the DLT assessment period. DLTs will be assessed during Part 1 using pre-specified AE criteria detailed in [Section 3.2.3](#).
- Type, incidence, and severity of adverse events (AEs) and serious adverse events (SAEs), deaths, dose reductions, treatment interruptions and discontinuations due to toxicity, and changes from baseline in clinical laboratory parameters. Adverse events will be graded for severity per the National Cancer Institute Common Terminology Criteria for Adverse Events (NCI CTCAE) version 5.0.
- Changes from baseline in physical examination, ECG, and ocular examination findings.

- Changes from baseline in vital sign (VS) measurements and pulse oximetry.
- Identification of the MTD or MAD.

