- Drug-induced liver injury (Hy's law), including all of the following: greater than $3 \times$ ULN elevation in aspartate aminotransferase (AST) and/or alanine aminotransferase (ALT), total bilirubin $>2 \times$ ULN in the absence of findings of cholestasis (ie, absence of alkaline phosphatase elevation to $>2 \times$ ULN) AND no other etiology to explain the combination of increased ALT/AST and total bilirubin.
- FBS >200 mg/dL on 2 consecutive measurements, at least 24 hours apart, over a 7-day period. In the DLT assessment period, subjects who experience FBS >200 mg/dL must have testing repeated within 7 days.

3.2.4. Definition of Maximum Tolerated Dose, Maximum Administered Dose, and Recommended Phase 2 Dose

The estimated MTD is the dose level associated with approximately 30% of DLT-evaluable subjects experiencing a DLT. The target interval for the DLT rate is 25%-35%. Due to the discreteness of the dose levels and in the interest of the safety of subjects, the estimated MTD is the highest tested dose level with a DLT rate $\leq 35\%$ in at least 6-12 DLT-evaluable subjects. In general, the highest dose in Part 1 that provides an acceptable safety profile (MTD or MAD) will also be the highest dose tested in Part 2 unless one or more of the following suggest that an alternate (ie, lower) dose would be preferable:

- Clinically significant anti-tumor effects observed at a lower dose.
- The frequent occurrence of late and relevant AEs that occur after the DLT period.

The MAD is declared without an MTD based on the highest dose level with an observed DLT rate $<25\%$ (the lower bound of the MTD range) and where sufficient safety and efficacy signals have been observed.

The RP2D is the dose chosen for further study based on assessment of a favorable benefit-risk profile across the totality of Phase 1 study results, including both Parts 1 and 2. The RP2D will

take into account late and relevant toxicities that occur after the DLT assessment period in Part 1 and/or the safety/tolerability of multiple cycles of treatment.

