#### Definition of MTD, MAD, and RP2D

The estimated MTD is the dose level associated with approximately 30% of DLT-evaluable subjects experiencing a DLT. The target interval for the DLT rate is 25%-35%. Due to the discreteness of the dose levels and in the interest of the safety of subjects, the estimated MTD is the highest tested dose level with DLT rate  $\leq 35\%$  in at least 6-12 DLT-evaluable subjects. In general, the MTD will equal the RP2D unless one or more of the following suggest that an alternate dose below the MTD would be preferable:

- Clinically significant anti-tumor effect.
- The MTD is not achieved, in which case the MAD may become the RP2D.
- The occurrence of late and relevant AEs that occur after the DLT period.
- Cumulative toxicity of the MTD or MAD, reflecting that the administration of multiple cycles at the MTD or MAD is not feasible.
- AEs observed beyond Cycle 1 that would require setting the RP2D below the MTD level.

The SRC will evaluate the totality of the events and consider whether they could result from a cumulative toxicity or are significant for the determination of the RP2D.

The MAD is declared without an MTD based on a dose level with an observed DLT rate <25% (the lower bound of the MTD range) and where sufficient safety and efficacy signals have been observed.

The RP2D is the dose chosen for further study based on Phase 1 study results. The RP2D will take into account late and relevant toxicities that occur after the DLT period and/or the cumulative tolerance of multiple cycles of treatment. If the MTD or MAD proves to be clinically feasible for long-term administration in a reasonable number of subjects, then this dose usually becomes the RP2D. Further experience with the MTD/MAD may result in a RP2D dose lower than the MTD/MAD (eg, if in the expansion part >25% of subjects require a dose reduction due to toxicity, then the sponsor may convene an SRC to determine if a lower RP2D needs to be determined).

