## **5. SAMPLE SIZE AND POWER CONSIDERATIONS**

The sample size for Part 1 will be approximately 70 subjects, but the actual sample size will depend on the number of dose levels of KZR-261, number of subjects per dose level, and the number of subjects treated at the MTD or the MAD(s) of KZR-261.

Dose escalation will continue accruing until one of the three stopping conditions below is triggered:

- The maximum sample size has been achieved,
- MTD/MAD has been identified with sufficient accuracy: data from 6 to approximately 12 subjects have been accumulated at a dose that is deemed to be the MTD/MAD, or
- All doses explored appear to be overly toxic and the MTD cannot be determined.

Due to binomial data variability in small samples, DLTs may be observed in a first cohort(s) by chance even when the true probability (DLT) is fairly low. This could result in the estimated posterior DLT rate exceeding the targeted 30% very early in the trial, triggering an early stop when very few subjects (2-4) have been treated. To prevent stopping the trial prematurely in such cases, a step-down option with a lower dose of 0.9 mg/m^2 is added to the dose grid. This dose

will be explored only if a high DLT rate occurs in the first cohort assigned to 1.8 mg/m^2, ie, it will not be used as a starting dose.

Upon identification of the MTD/MAD at the conclusion of Part 1, the study will continue with up to 4 tumor-specific expansion cohorts and 1 All-Tumors cohort in Part 2A. As previously noted, the tumor-specific cohorts (n = 15 at interim) may be increased up to 35 subjects per cohort to more precisely estimate the anti-tumor activity of KZR-261, if there is a sufficient efficacy signal at the interim analyses ([Protocol Section 10.6](#)) and if the tumor type is not selected for investigation in Part 2B (dose optimization). The All-Tumors cohort may enroll up to 35 biopsy-evaluable subjects.

Go/No-Go futility analysis for each tumor-specific cohort in Part 2A will be based on CBR as the primary outcome measurement (as defined in [Protocol Section 10.5.5](#)) after Stage 1 enrollment of 15 subjects. Each of the expansion cohorts is based on the following assumptions:

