## 12. MTD ESTIMATION AND DLT ANALYSES

In the dose escalation part,  $(x_d, n_d)$  will be observed for  $d=1, \dots, K$ , where  $d$  represents dose levels and  $K$  represents the total number of dose levels. Assuming  $n_d$  subjects have been treated at dose  $d$ , and  $x_d$  of them experienced DLTs, let  $x_d|p_d \sim \text{Bin}(n_d, p_d)$  and  $p_d \sim \text{Beta}(0.005, 0.005)$ . The posterior mean toxicity probability at dose  $d$  is estimated as,

$$\hat{p}_d = \frac{x_d + 0.005}{n_d + 0.01}$$

Isotonic regression will then be applied to the posterior mean DLT rates. Let  $\tilde{p}_d$  represent the isotonic-transformed posterior means for all the doses. The MTD will be the dose that satisfies  $\tilde{p}_d \leq 0.35$  and is closest to the target rate of 0.30. If multiple such doses satisfy the criteria, MTD will be the highest dose level that is  $\tilde{p}_d \leq 0.30$ . If no such doses, MTD will be the lowest dose that is  $\tilde{p}_d > 0.30$ .  $\tilde{p}_d$  is estimated using Pool-Adjacent-Violators Algorithm (PAVA), a solution to isotonic regression.

DLTs will be listed and summarized by MedDRA system organ class and preferred term. The DLT analysis set will be used for summaries.

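### The protocol and SAP give non-equivalent rules for the MTD, a Part 1 primary endpoint, so the same DLT data can name different doses depending on the section read

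*Protocol*

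**What the plan says.** "Identification of the MTD or MAD" is a Part 1 primary endpoint (Protocol 2.2.1.1). The selection rule appears in three forms.

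- **Rule A** (Protocol synopsis, Protocol 3.2.4, SAP 4.1.1). After a general description, "The estimated MTD is the dose level associated with approximately 30% of DLT-evaluable subjects experiencing a DLT", the operative text in Protocol 3.2.4 is that "the estimated MTD is the highest tested dose level with a DLT rate" of at most 35% in at least 6-12 DLT-evaluable subjects. SAP 4.1.1 repeats it: "the estimated MTD is the highest tested dose level with DLT rate" of at most 35%, with the same 6-12.
- **Rule B** (Protocol 10.5.2). The MTD is the dose whose rate is "closest to the prespecified target DLT rate and within the equivalence interval (EI", that is, 0.25 to 0.35. The same sentence then gives a formula: minimise the distance of the isotonic posterior mean from 0.30 over all doses with at least one treated subject and Pr(p > 0.30) below the cut-off, which Protocol 10.5.1 sets at 0.95. The formula has no interval limit, no 35% ceiling and no minimum number beyond one.
- **Rule C** (SAP 12). The isotonic posterior mean must be at most 0.35 and closest to 0.30. There is no minimum number of subjects and no Pr filter. If several doses qualify, the highest at or below 0.30 is taken. Then: "If no such doses, MTD will be the lowest dose that is" above 0.30.

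SAP 1 says its methods supersede those of the protocol. SAP 19 declares no changes from the protocol. Protocol 10.1.1 and SAP 5 both allow Part 1 to stop because "All doses explored appear to be overly toxic and the MTD cannot be determined".

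**The concern.** A primary endpoint should follow from the data by one stated rule. Here the sections differ on five things: raw or isotonic rates; highest qualifying dose or dose closest to 0.30; whether a 0.25 floor applies (only in the first half of Rule B); whether a minimum number of subjects applies (only in Rule A); and whether the Pr filter applies (only in Rule B). Rule B also contradicts itself, since its formula can select a dose that its opening condition excludes.

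The precedence clause in SAP 1 may put C over B. It cannot choose between A and C, because both are in the SAP. SAP 19 is inaccurate as long as SAP 12 differs from Protocol 10.5.2.

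The MTD or MAD is the reference dose for Part 2A and Part 2B. If the rules name different doses, a reader of the report could not tell which rule produced the declared one.

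**Working it through.** **Inputs.** Target 0.30 and interval [0.25, 0.35] (Protocol 3.2.1); cut-off 0.95 (Protocol 10.5.1); posterior mean (x + 0.005)/(n + 0.01), followed by pool-adjacent-violators (SAP 12). Two assumptions are needed for Rule B. The SAP posterior mean is used for its isotonic estimate. A Beta(1,1) prior is used for Pr(p > 0.30), because Protocol 10.5.2 states none. The minimum in Rule A is taken as 6, the lower end of 6-12.

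**The plan's own figure.** The documents give no operating characteristics for MTD selection, so the only computed Part 1 figure is the decision table (Table 1). Comparing x/n and (x-1)/n with the interval, and marking DU when Pr(p > 0.30) > 0.95, reproduces all 90 cells with Beta(1,1). With the SAP's Beta(0.005, 0.005) it reproduces 89 of 90 (5/9 becomes D instead of DU). This supports the assumed prior.

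**Same data, each rule.** Doses are in ascending order. In the first, second and fourth rows a lower dose with 0/3 precedes the doses shown and is never chosen.

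| DLTs/subjects | Isotonic means | Distance from 0.30 | Rule A | 10.5.2 with interval | 10.5.2 formula only | Rule C |
|---|---|---|---|---|---|---|
| 2/7, 2/6 | 0.286, 0.334 | 0.014, 0.034 | higher | lower | lower | lower |
| 1/6, 1/3 | 0.167, 0.334 | 0.133, 0.034 | lower | higher | higher | higher |
| 1/6, 4/8, 2/6 | 0.167, 0.429, 0.429 | 0.133, 0.129, 0.129 | third | none | second | first |
| 0/6, 3/6 | 0.001, 0.500 | 0.299, 0.200 | lower | none | higher (50%) | lower |
| 3/6, 3/6 (only doses) | 0.500, 0.500 | 0.200, 0.200 | none | none | lowest (50%) | see below |

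Details:
- Row 1: 2.005/7.01 = 0.286 and 2.005/6.01 = 0.334. Both raw rates (28.6%, 33.3%) are at most 35%, so A takes the higher dose.
- Row 2: A excludes the second dose because it has only 3 subjects.
- Row 3: the upper two doses are pooled, (8 × 0.500 + 6 × 0.334)/14 = 0.429. The formula has a tie above 0.30 and so takes the lower of the two. Pr(p > 0.30) for 4/8 is 0.90, so the filter does not remove it. A uses the raw 33.3% at the third dose.
- Row 4: Pr(p > 0.30) for 3/6 is 0.874, below 0.95, so the formula keeps the 50% dose and prefers it.
- Row 5: no dose has a mean at or below 0.35. Read literally, SAP 12 names the lowest dose, at 50%. Read as a tie-break, it names none.

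**How often.** Simulated i3+3 escalation under assumed toxicity curves (cohorts of 2-4, at most 70 subjects, stopping at 6 or 12 at a dose, with and without backfill, 3000 trials per setting) gave, when a tolerable dose existed:
- A and C differed in about 1-5% of trials. With cohorts of 3 and no backfill the figure was 0%.
- The 10.5.2 formula alone named a dose with an isotonic mean above 35% in about 17-24%. Another set of runs, with cohorts of 3 and counting observed rates above 35%, gave 6-13%.

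With every dose assumed at 45% DLT or more, Rule A named no MTD in about 59-74% of trials. The literal SAP 12 sentence named a dose above 35% in about 55-73%.

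**The case against.** Four arguments limit the point.

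1. **The MAD absorbs many cases with no MTD.** A reader might infer that 10.5.2 with the interval often sends Part 2 to a different dose, because it often names no MTD where 3.2.4 names one. That does not follow. Protocol 3.2.4 defines the MAD as the highest dose with an observed rate below 25%, and the endpoint is MTD or MAD. In simulations with cohorts of 3 and no backfill, every trial in which the interval left no MTD but Rule A named one had a Rule A dose below 25%, the same dose that the MAD rate criterion selects. The difference is then mainly the label, subject to the MAD's further condition of sufficient safety and efficacy signals.

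2. **Precedence.** If SAP 1 puts SAP 12 over Protocol 10.5.2, the largest divergence drops out and the A-versus-C conflict remains, which is rare. This stands as to size, but the plan still has two rules.

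3. **The SAP 12 sentence may be only a tie-break.** It resembles the tie rule in Protocol 10.5.2, and SAP 5 supports that reading. A reader might infer that the SAP certainly names a dose above 35%. The text allows this but does not establish it.

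4. **Some examples are unusual.** Table 1 says stay at 1/3, so enrolment would normally continue. 1/6, 4/8, 2/6 needs backfill or re-escalation. 2/7 then 2/6 also depends on backfill, which Protocol 3.2.1.1 allows. After 0/6 at the lower dose Table 1 reads escalate, so 0/6 then 3/6 is final only if accrual stops there. The examples show that the rules differ; they do not show how often.

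A reader might also infer that the MTD fixes the dose for all 175 + 120 = 295 possible Part 2 subjects. It does not. About half of Part 2B (60 of 120) is randomised to a lower dose, SAP 4.1.2 allows a dose recommended by the SRC, and Protocol 3.2.4 allows a lower dose in Part 2.

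**Conclusion.** The point holds. The documents carry three MTD rules that are not equivalent, one of which contradicts itself, and neither SAP 1 nor SAP 19 resolves them. The worked examples follow from the text, apart from the two stated assumptions for Rule B. In the 0/6 then 3/6 example the 50% dose also passes the filter with the SAP's own prior (Pr = 0.837).

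The size is uneven. A and C seldom disagree when a tolerable dose exists (about 0-5%). The larger gap comes from Protocol 10.5.2, whose formula can exceed 35% without any help from the SAP sentence. That sentence matters mainly if every dose is too toxic, and only on its literal reading. All percentages rest on assumed toxicity curves and trial conduct and are illustrative. The text should be settled before an MTD or MAD is declared, because a primary endpoint cannot be reproduced from the plan as written.

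**What to change.** Reconcile the passages to one selection rule, worded identically in the Protocol synopsis, Protocol 3.2.4, Protocol 10.5.2, SAP 4.1.1 and SAP 12. The rule should state:

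- whether raw or isotonic rates are used, and whether the highest qualifying dose or the one closest to 0.30 is taken;
- whether the 0.25 floor applies;
- the minimum number of evaluable subjects, as one number in place of 6-12;
- whether the Pr < 0.95 filter applies and, if so, with which prior;
- how the rule hands over to the MAD when no dose meets the MTD condition.

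Limit the last selection sentence of SAP 12 to ties among doses that already qualify, and state that no MTD is declared if none does, in line with SAP 5. Correct SAP 19 so that it lists any remaining difference from the protocol.

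The cost is wording in five places plus SAP 19. No new data, subjects or procedures are needed.

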10.5.3. Simulations and Operating Characteristics of the i3+3 Design

Other than the slightly different decision tables (see (Liu et al., 2020) [Figure A1 in Appendix D]), the i3+3, mTPI, and mTPI-2 designs use the same safety rules and same inference to select the MTD. Because the mTPI and mTPI-2 designs have been well established in the literature with desirable performance, as indicated by the authors (Liu et al., 2020), there is no need to conduct more and larger simulations, such as a simulation study with 1,000 random scenarios, to further evaluate the operating characteristics of the i3+3 design. The i3+3 design is expected to perform at a similar level as the mTPI and mTPI-2 designs due to its similar but slightly improved decision table, which puts i3+3 in par with other major model-based designs.

10.5.4. Safety Analysis

Safety analyses will be performed for all subjects who received at least 1 dose of study drug.

Prior and concomitant medications will be coded using the WHO Drug dictionary (version March 2023 or later). Verbatim AE terms will be coded using the Medical Dictionary for Regulatory Activities (MedDRA) (version 26.0 or later). All AEs that occur after administration of the first dose of study drug and through 30 days after last dose of study drug will be considered treatment-emergent adverse events and will be summarized by MedDRA system organ class and preferred term. The incidences (percentages) of subjects experiencing each AE preferred term will be summarized. AEs will also be summarized by severity in accordance with NCI CTCAE v5.0 and by causality (relationship to study treatment). DLTs, AEs, Grade 3, Grade 4, and Grade 5 AEs, SAEs, and AEs resulting in dose reductions, treatment interruptions, or treatment discontinuation will be summarized by MedDRA preferred terms. Deaths that occur after the first dose of study drug and through 30 days after the last dose of study drug will be considered “on treatment” deaths and will be summarized. All deaths will be listed.

Clinical laboratory, vital sign measurements, and ECG data will be summarized descriptively (means, medians, standard deviations, and minimum and maximum values) by dose/treatment group and overall and at protocol-specified time points along with a summary of change from baseline at each protocol-specified time point.

Incidence of clinical laboratory abnormalities will be summarized with descriptive statistics. Vital signs and physical examination results will be summarized with descriptive statistics. Changes from baseline in physical and ocular examination findings will be listed and described for each subject.

